	Appendix V Interventions for Active Group	
	Appendix VI Patient Data Collection: Questionnaires and Diaries	
	Appendix VII Dummy Tabulations – Draft	
	Appendix VIII Plan of Study Events and Progress	
	Appendix IX Publication Policy	
	Appendix X Membership of Maps Study	
	Appendix XI Terms of Reference for TSC and DMC	

PROTOCOL SUMMARY

QUESTION ADDRESSED	Does conservative (physical) treatment improve urinary incontinence in men who have had prostate surgery?
CONSIDERED FOR ENTRY	Men who have urinary incontinence after prostate surgery, approached initially when inpatients having surgery.
POPULATIONS	1. Radical Prostatectomy (RP) 2. Transurethral Resection of Prostate (TURP)
STUDY ENTRY	
Information about all men having prostate surgery collected by recruitment officers in centres, sent to MAPS Study Office.
 
Screening postal questionnaire sent from MAPS Study Office at 3 weeks after surgery.
 
Consent to RCT obtained from incontinent men after written and oral information, and after completing Baseline Questionnaire and Urinary Diary.

INTERVENTIONS	
Active group attend four treatment sessions during 3-month period after randomisation (pelvic floor muscle training with biofeedback, bladder training)
 
Control group do not have active treatment
 
Both groups receive Lifestyles Advice Leaflet

OUTCOME ASSESSMENT	
Postal questionnaires at 6 and 12 months after randomisation
 
Urinary diaries (incontinent episodes and pad use) and health care utilisation questions at 3, 6, 9 and 12 months

CO-ORDINATION	
Local: by local lead Urologist and Recruitment Officer.
 
Central: by Study Office in Aberdeen ([contact]).
 
Overall: by the Project Management Group, and overseen by the Steering Committee and the Data Monitoring Committee.

FUNDING	NHS R&D National Coordinating Centre for Health Technology Assessment (NCCHTA).
Start date:	December 2004
Planned finish date:	February 2010
Planned reporting date:	February 2010

MAPS PERSONNEL

Grant Holders / MAPS Project Management Group

[name], [name], [name], [name], [name], [name], [name], [name], [name], [name], [name], [name]

Steering Committee Independent Members

Chair [name], Urologist, Bristol
Others [name], Economist, York
[name], Senior Physiotherapist, St Ives, Cambridgeshire
[name], Patient Representative, Bristol

Data Monitoring Committee Members

Chair [name], Professor of Stroke Care, Glasgow
Others [name], Methodologist, Leeds
[name], Urologist, Stevenage, Herts
[name], Nurse Consultant, Harrow, London

MAPS Study Office Team in Aberdeen

[name], [name], [name], [name], [name], [name], [name], [name], [name], [name].

Other Information

International Standard Randomised
Controlled Trial Number (ISRCTN) ISRCTN87696430
MREC Reference Number MREC/04/10/01
MREC Version Number Version 6, 01 07 07
HTA Project Number 03/14/03

Trial Registrations

The NHS HTA Programme website <http://www.hta.nhsweb.nhs.uk/projectdata>

The CancerHelp UK website: www.cancerhelp.org.uk

INVOLVE www.invo.org.uk

National Cancer Research Network Trials Portfolio: NCRN Trial ID 1459

Current Controlled Trials website: ISRCTN87696430

NIH website: ClinicalTrials.gov Identifier: NCT00237029

CONSERVATIVE TREATMENT FOR URINARY INCONTINENCE IN MEN AFTER PROSTATE SURGERY

Known as MAPS (Men After Prostate Surgery)

Title of trial: Conservative treatment for urinary incontinence in men after prostate surgery (MAPS): multicentre randomised controlled trial of pelvic floor muscle training, biofeedback and bladder training

This protocol describes a major multicentre UK trial to establish whether conservative physical treatment delivered personally by a trained health professional results in better urinary and other outcomes compared with standard management in men who are incontinent after prostate surgery. The study is designed to be as simple as possible both for those participating and for those involved in clinical care.

Recruitment officers in each centre will identify and recruit men undergoing prostate surgery and collect descriptive information. Those who are incontinent will be invited to enter a randomised trial of conservative treatment. They will be followed up at 6 and 12 months.

1. THE REASONS FOR THE TRIAL

1.1 The burden of the problem

Prostate surgery is an iatrogenic cause of male urinary incontinence. Urinary incontinence is defined as the complaint of any involuntary leakage of urine.¹ It is a debilitating condition that has a greater effect on quality of life than erectile dysfunction (which is another consequence of prostate surgery).² The economic costs include personal (such as need to use pads or devices, and deleterious effect on quality of life) and societal ones (use of health services and need for residential or nursing home care).

Based on a population audit of over 3000 men, an estimated 11% of men needed to use pads at 3 months after endoscopic resection of prostate.³ The prevalence of urinary incontinence after radical prostatectomy is more widely reported, ranging from 5% to 45%, albeit at varying times after operation.⁴ Estimates of incontinence soon after radical operation are much higher (e.g. 82% in 1013 men⁵). We have used estimates of 5% and 50% respectively in calculation of sample sizes (which may be conservative, based on data from a feasibility study).

1.2 The decision to test conservative treatment

A recent Cochrane review has identified that, although conservative treatment based on pelvic floor muscle training may be offered to men with urinary incontinence after either type of prostate surgery, there is insufficient evidence to evaluate its effectiveness, cost-effectiveness and effect on quality of life.⁶ Data from three trials involving 232 men provided estimates of the effects of pelvic floor muscle training on the chance of incontinence after radical prostatectomy at 1 year: relative risk (RR) for incontinence, pelvic floor muscle training plus biofeedback versus control, 0.55, 95% CI 0.24 to 1.23.⁷⁻⁹ However, not all of the men included in the trials were incontinent at baseline, and the trials were all small. Thus the data suggest (but do not provide conclusive evidence) that conservative treatment may reduce incontinence at 1 year after operation.

Data available from these trials suggest that, amongst men incontinent at around 6 weeks after surgery, about 30% will still be incontinent at 1 year. The Cochrane review therefore suggests that this might be reduced to 15%, and this is the basis for the sample size in the proposed trial (70% 'dry' increased to 85% 'dry').

In one small trial of pelvic floor muscle training started before surgery amongst men having endoscopic resection of prostate, the RR for incontinence at 4 weeks after surgery was 0.31, 95% CI 0.03 to 2.82¹⁰ although again the trial included some men who were not incontinent at baseline. After the first 4 weeks, there were no trial data about expected incontinence rates or effect sizes amongst men having endoscopic resection of prostate.

1.3 The questions which this study will address

The following questions will be addressed, primarily in terms of regaining urinary continence at 12 months after recruitment:

- (a) For men with urinary incontinence 6 weeks after radical prostatectomy, what is the clinical and cost-effectiveness of active conservative treatment delivered by a specialist continence physiotherapist or a specialist continence nurse compared with usual management?
- (b) For men with urinary incontinence 6 weeks after transurethral resection of prostate, what is the clinical and cost-effectiveness of active conservative treatment delivered by a specialist continence physiotherapist or a specialist continence nurse compared with usual management?

The hypothesis being tested in each group of men (in two parallel but separate trials) is that active conservative management will increase the proportion of continent men by 15% at 1 year after recruitment. The two groups are being considered independently because the rates of incontinence are expected to be different.

2. TRIAL RECRUITMENT AND ALLOCATION

2.1 Men considered for trial entry

The trial will involve men who have urinary incontinence after prostate surgery. Two parallel but separate trials will be conducted, amongst:

- (i) men having a radical prostatectomy usually for prostate cancer, and
- (ii) men having a transurethral resection of prostate, usually for benign prostatic hypertrophy.

Inclusion criteria:

- Urinary incontinence at 6 weeks after prostate surgery (incontinence defined as a response indicating a loss of urine to either of two questions in the screening questionnaire: 'how often do you leak urine' and 'how much urine do you leak').
- Informed consent.
- Ability to comply with intervention.

Exclusion criteria:

- Referral for formal therapy (teaching of pelvic floor muscle training) because of prostate surgery.
- Radiotherapy planned or given during the first 3 months after surgery for men with prostate cancer.
- Endoscopic resection of prostate carried out as palliation for outflow obstruction in advanced prostate cancer.
- Inability to complete study questionnaires.

Men with prostate cancer diagnosed at TURP:

Around 15% of men may be found to have incidental prostate cancer when the prostatic chips removed at TURP are examined for pathology. If he is not going to have formal treatment (wait and see policy), he will be eligible for the RCT.

If the cancer is identified before he is randomised and either radiotherapy or radical prostatectomy are planned, he will **not** be eligible for the RCT (TURP group). However, if he is subsequently readmitted for radical prostatectomy, he will be

eligible to be recruited as a new participant to the Radical group. He would sign a new consent form and be sent a new screening questionnaire.

If the cancer is only diagnosed once he has been randomised, even if radiotherapy or radical prostatectomy are planned, he will remain in the group to which he was allocated, and be followed up as normal.

The study consists of two stages: Stage 1 (Section 2.2) concerns the screening survey used to identify eligible men, and Stage 2 (Section 2.3) the randomised controlled trial.

2.2 Screening for postoperative urinary incontinence (Stage 1 of study)

Potential participants will be identified by Recruitment Officers in each clinical centre from amongst all men admitted to the urological ward(s) for prostate surgery. A log will be kept of men meeting the inclusion criteria, describing reasons if they do not agree to receive a screening questionnaire (Appendix 1).

Each man will be given the Hospital Patient Information Sheet by the Recruitment Officer. After reading it and having the opportunity to discuss all aspects of the study, each man will be asked for his consent to be sent the Screening Questionnaire at 3 weeks after surgery. The patient information sheet, the consent form and the questionnaire all refer to the possibility of being contacted about further research if the men are willing. If he agrees, his signed contact details (address, phone number, date of birth, Study Number and Hospital Number) will be sent to the Study Office in Aberdeen (Appendix I).

The questionnaire (Appendix VI) will be sent to men from the Study Office in Aberdeen at 3 weeks after the date of operation (together with a covering letter, Appendix II). A reminder letter will be sent after 2 weeks if there is no response (Appendix II). If the returned questionnaire indicates that a man has urinary incontinence, he will be eligible for Stage 2.

2.3 Recruitment to the RCT of conservative treatment (Stage 2, the trial)

Each man with urinary incontinence will be sent a Patient Information Sheet (PIS, Appendix III) by the Study Office in Aberdeen to inform him about the trial.

- *For men who have a phone*

The Aberdeen Recruitment Co-ordinator will send the man a Patient Information Sheet (Appendix III) by post, with a consent form, Baseline Questionnaire and Urinary Diary. About a week after sending the trial information and documents, she will contact the man by telephone using a Standard Instruction Sheet (Appendix III). She will ask if he has received the Patient Information Sheet, answer any questions or concerns, and ask whether he might be interested in entering the trial. She will explain what would happen in the two groups, that allocation would be randomised and what follow-up is involved. If he agrees orally, he will be asked to complete and return: a Consent Form (Appendix III); a Baseline Questionnaire (Appendix VI); and a Urinary Diary (Appendix VI). Optionally, the man may fill in the Baseline Questionnaire over the phone but written consent is still required before randomisation.

- *For men who do not have a phone:*

All the documents [the Patient Information Sheet (Appendix III), a Consent Form (Appendix III), a Baseline Questionnaire (Appendix VI) and a Urinary Diary (Appendix VI)] will be sent by mail. The man will be able to ring a helpline (to the Aberdeen Recruitment Officer) if he has any queries. If he decides to enter the trial, he will complete and return the last three documents.

The man would keep the Information Sheet and the bottom (fourth) copy of the consent form (returning the top three to the Study Office in Aberdeen).

If the three documents are not returned by 3 weeks after posting (no phone contact), or 2 weeks after oral consent was given over the phone, men will be sent a postal reminder with duplicate documentation. If they are not returned after another 2 weeks, they will be phoned (if possible) or sent a further reminder letter (if no phone).

Oral Withdrawal Consent will be obtained from men who initially agree to enter the trial but later decide to withdraw to enable us to maintain their existing data and access NHS data.

2.4 Randomisation and allocation to management group

When the baseline documents are received, the Aberdeen MAPS Study Office will randomise the man to active or standard management.

Randomisation will be by computer allocation using the service that already exists at the Health Service Research Unit. Allocation will be stratified by type of operation (radical prostatectomy or transurethral resection of prostate), and minimised using centre, age and pre-existing urinary incontinence.

The Study Office will send out an allocation letter to all men with details of their allocation (Appendix IV) and the Lifestyle Advice Leaflet (Appendix V). If the man is allocated to the Active Group, the Study Office will arrange for the local Therapist (physiotherapist or continence nurse) to send him the necessary appointments (the first, for an hour, as soon as possible, followed by a three-quarter-hour appointment on three occasions at 2, 6 and 12 weeks) (letter to Therapist, Appendix IV).

A letter and GP Information Sheet (Appendix IV) will be sent to the man's GP. A copy of the GP letter and the consent form will be sent to the hospital urological consultant for filing in the man's hospital notes.

3. TRIAL INTERVENTIONS (Appendix V)

3.1 Intervention arm

The men in the intervention group will receive a physiotherapist or continence nurse assessment of their symptoms at about 6 weeks after surgery. They will be taught pelvic floor muscle training, with bladder training for men with urgency or urge incontinence.¹¹ The men will be taught:

- to carry out three maximum pelvic floor contractions in three positions (standing, sitting and lying down) twice per day;
- to 'lift' their pelvic floors while walking;
- to tighten their pelvic muscles before activities which may cause them to leak, such as coughing;
- and to tighten after urinating to 'squeeze out' any last drops.

Biofeedback involves monitoring the strength of a pelvic floor contraction (by digital anal assessment) and relaying the information back to the men, in order that they know when they are performing contractions correctly and to inform them when they are increasing the strength or duration of their contractions. Therapists may use machine-mediated biofeedback with an anal biofeedback probe at their clinical discretion (if they feel it is clinically indicated) in centres where this is available in addition to digital anal assessment. Bladder training involves gradually delaying urination (by pelvic floor muscle contraction and distracting activities) to teach the bladder to hold increasing volumes of urine.

The men will also receive a booklet describing pelvic floor muscle training (Pelvic Floor Exercise Booklet, Appendix V) in addition to the one giving general lifestyle advice (Lifestyle Advice Booklet, Appendix V). The men will have reinforcement

sessions on three more occasions over 3 months – at around 2 weeks, 6 weeks and 12 weeks after the first appointment.

Ensuring standardisation of intervention

All the staff delivering the intervention will receive training to ensure consistency of their method of teaching and delivery of the pelvic floor muscle training, bladder training and biofeedback. Both specialist continence physiotherapists and continence nurse specialists will be eligible for training, thus extending the generalisability of the trial.

The therapists will record their assessments and treatment programmes on standard study forms (Appendix V). Data from these forms will be collected centrally.

3.2 Control arm

Men in the control group will receive a booklet containing supportive lifestyle advice only (without reference to pelvic floor muscle training) by post after randomisation (Lifestyle Advice Booklet, Appendix V). Men will not receive any formal assessment or treatment but will be able to access usual care and routine NHS services if they feel they need help. This may include written advice if this is part of routine hospital care.

Use of NHS services, use of pads and practice of pelvic floor muscle training will be documented in both groups using information from questionnaires and Urinary Diaries. The lifestyle and pelvic floor muscle training booklets will be customised for each group.

4. SUBSEQUENT ARRANGEMENTS

4.1 Informing key people

Following formal trial entry, the Study Office will contact:

- i) The General Practitioner (by letter enclosing an information sheet, with the MAPS phone number in case of queries or notifiable events)
- ii) The Hospital Urologist (by copy of letter sent to GP, and copy of consent form for filing in hospital notes)

4.2 Monitoring the men

Men will be contacted by phone, post or email as appropriate. In case of non-return of questionnaires or diaries, or non-attendance at therapy appointments, attempts will be made by staff at the Study Office to trace the men directly using these means or indirectly by contacting the therapist, the GP or the 'Best Contact'.

Notification by GPs

GPs are asked to phone the Study Office if one of the participants moves, becomes too ill to continue or dies, or any other notifiable event or possible adverse effect occurs. Alternatively, staff at the Study Office may contact the GP.

Notification by 'best contact'

If the MAPS Study Office loses touch with a participant (e.g. questionnaires, diaries or phone calls not returned), we will try to establish why via the 'Best Contact'. Men will be asked (in their trial Baseline Questionnaire) to nominate someone, who will be informed (Appendix IV).

Flagging at Office for National Statistics

All men recruited to the RCT will be flagged at the Office for National Statistics for notification of death.

5. DATA COLLECTION AND PROCESSING

Men will be recruited for a median period of 2 years (range 1–3). Follow-up will continue for 15 months from the date of the last operation (allowing 3 months for recruitment and 12 months for follow-up after randomisation). It is not part of this protocol or the current study to follow up the men beyond this time. However, consent will be sought to make this possible in the future.

5.1 Questionnaires (Appendix VI)

Men will be sent questionnaires at baseline, 6 and 12 months (Appendix VI). Content will include:

- i) Urinary outcome questions [leakage of urine, amount, effect on QOL (<http://www.icIQ.net/>), pad use, catheter use]
- ii) Bowel function outcome questions
- iii) Sexual function
- iv) Health care utilisation questions
- v) Exercise, weight and height, including pelvic floor exercises
- vi) EQ-5D¹²
- vii) SF-12¹³

and additionally at baseline only:

- i) Date of operation, type of operation and reason for operation
- ii) GP address and phone number
- iii) 'Best Contact' at another address for follow-up (not wife or partner)
- iv) Other medical problems

and additionally at 6 months only:

- i) Health Care Unit Cost Questionnaire

and additionally at 12 months only:

- i) Need for further treatment for incontinence
- ii) Further treatment for prostate planned?

5.2 Urinary diaries (Appendix VI)

Men will be asked to keep diaries at 3, 6, 9 and 12 months, kept for 3 days at each time period. Content will include:

- i) Frequency of urination (day and night)
- ii) Daily episodes of incontinence, quantity of loss
- ii) Daily use of pads, need to change clothing or bedding

and additionally at 3 and 9 months only:

- iii) Health care utilisation questions (Appendix VI)

5.3 ISD Data (Scotland only)

At 6 months after the last man has been recruited we will run a check for Scottish men only to compare self-reported operations, diagnoses and hospital admissions with centrally collected data to validate a proportion of the data.

5.4 Data processing

Data from the various sources outlined above will be sent to the Study Office in Aberdeen for processing. Staff in the Study Office will work closely with local Recruitment Officers to ensure that the data are as complete and accurate as possible. Extensive range and consistency checks will further enhance the quality of the data.

6. ANALYSIS PLANS

6.1 Ground rules for the statistical analysis

The statistical analysis will be based on all men as randomised, irrespective of subsequent compliance with the treatment allocated. The principal comparisons will be:

1. After radical prostatectomy
 - i) men allocated to active therapy (four visits to therapist plus Lifestyle Advice Leaflet), compared with
 - ii) men allocated to control group (Lifestyle Advice Leaflet only)
2. After transurethral resection of prostate
 - i) men allocated to active therapy (four visits to therapist plus Lifestyle Advice Leaflet), compared with
 - ii) men allocated to control group (Lifestyle Advice Leaflet only)

6.2 Measures of outcome

The primary clinical outcome is:

- Subjective report of urinary continence at 12 months (<http://www.iciq.net/>)

The primary measure of cost-effectiveness is:

- Incremental cost per quality-adjusted life-year

Secondary outcome measures include:

Clinical

- Subjective report of continence or improvement of urinary incontinence at 3, 6 and 9 months after randomisation, and improvement at 12 months
- Number of incontinent episodes in previous week (objective, from diary)
- Duration of incontinence (based on time of resolution relative to time of operation and randomisation)*
- Use of absorbent pads, penile collecting sheath, bladder catheter or bed/chair pads
- Number and type of incontinence products used
- Co-existence, cure or development of urgency or urge incontinence
- Urinary frequency
- Nocturia
- Faecal incontinence (passive or urge)
- Other bowel dysfunction (urgency, constipation, other bowel diseases)
- Sexual function at 12 months (including information about erection, ejaculation, retrograde ejaculation, pain, change in sex life and reason for change)

Quality of life

- Incontinence-specific quality of life outcome measure (10-point scale, ICI questionnaire (<http://www.iciq.net/>))
- General health measures (SF-12,¹³ EQ-5D¹²)

Use of health services for urinary incontinence

- Need for alternative management for incontinence (e.g. surgery, drugs)
- Use of GP, nurse, consultant urologist, physiotherapist

Other use of health services

- Visits to GP
- Visits to practice nurse

* We will obtain an estimate from the men who become dry of when they became dry – both by asking them to name the month they were last wet, and for how many months after their operation were they wet, as well as by the change in the 3-monthly diaries, from wet to dry.

Effects of interventions

- Use of PFMT
- Lifestyle changes (weight, constipation, lifting, coughing, exercise)

Economic measures

- Patient costs [e.g. self-care (e.g. pads, laundry), travel to health services, sick leave]
- Cost of conservative trial treatment
- Cost of alternative or additional NHS treatments [e.g. pads, catheters, drugs (e.g. adrenergic agonists, anticholinergics, oral medication for erectile dysfunction), hospital admissions or further surgery]
- Other measures of cost-effectiveness (e.g. incremental cost per additional man continent at 12 months)

The ways in which these data will be analysed are set out in Appendix VII (Dummy Tabulations).

It is anticipated that the data generated by the study, along with other focused data collection sets, may be used as a basis for exploratory or epidemiological research, but these will be described in separate protocols.

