6.5.5 Cost-effectiveness

Effectiveness within the trials will be measured in terms of quality-adjusted life-years (QALYs) and subjective continence at 12 months (assessed using data from the ICI questionnaire). QALYs will be estimated by combining estimated quantity of life, with quality of life derived from the EQ-5D questionnaire (administered at baseline, 6 and 12 months) and UK tariffs. The estimation of QALYs will take account of the mortality of study participants. Participants who die within the study follow-up will be assigned a zero utility weight from their death until the end of the study follow-up. QALYs before death will be estimated using linear extrapolation between the QALY scores at baseline and all available EQ-5D scores up to death. The method of eliciting QALYs described is one commonly adopted in economic evaluation.

The primary analysis is based on the 1-year follow-up of the trial and two outcomes have been specified. These are incremental cost per additional man continent and incremental cost per QALY. The former outcome has been chosen to facilitate understanding of the findings amongst health care professionals while the second measure, the primary economic outcome, has been chosen to reflect a societal decision-making perspective. The results will be presented as point estimates of mean incremental costs, proportion of men continent, QALYs, and cost per man continent or per QALY. Measures of variance for these outcomes are likely to involve bootstrapping estimates of costs, proportion of men continent, QALYs, and incremental cost per additional man continent and per QALY. Incremental cost-effectiveness data will be presented in terms of cost-effectiveness acceptability curves (CEACs).

Other forms of uncertainty, e.g. concerning the unit cost of a resource, will be addressed using standard deterministic sensitivity analysis. The results of the sensitivity analyses will also be presented as CEACs. Further sensitivity analysis will be conducted to consider the effect of differential timing over which treatments may be given. These data are likely to prove useful for the economic model.

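### The subjective continence outcome at 3 and 9 months has no matching question in the described schedule; as written, only the diary, a different measure, could supply it

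*Protocol*

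**What the plan says.** Section 6.2 of the protocol gives this secondary clinical outcome: "Subjective report of continence or improvement of urinary incontinence at 3, 6 and 9 months after randomisation, and improvement at 12 months". The next item in the same list is the number of incontinent episodes, which is attributed to the diary and labelled objective.

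The data collection is described elsewhere:

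- **Questionnaires.** Section 5.1 states: "Men will be sent questionnaires at baseline, 6 and 12 months (Appendix VI". The Protocol Summary agrees: "Postal questionnaires at 6 and 12 months after randomisation". The first content item in section 5.1 is "Urinary outcome questions [leakage of urine, amount, effect on QOL", together with pad and catheter use.
- **Diaries.** Section 5.2 states: "Men will be asked to keep diaries at 3, 6, 9 and 12 months, kept for 3 days at each time period". The listed content is frequency of urination, "Daily episodes of incontinence, quantity of loss", and pads and changes of clothing or bedding. Then, "and additionally at 3 and 9 months only", come health care utilisation questions.
- **Source of subjective continence.** Section 6.5.5 speaks of "subjective continence at 12 months (assessed using data from the ICI questionnaire".

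**The concern.** An outcome described as a subjective report needs a question that asks for one. On the described content, men are asked about leakage by questionnaire at 6 and 12 months but not at 3 or 9 months. The 3-month reading matters because therapy runs to about 12 weeks after the first appointment (sections 2.4 and 3.1), so it is the scheduled reading nearest the end of treatment.

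Two things are at stake. If no item is asked at 3 and 9 months, no analysis plan can recover it later. If the diary is used in its place under the same outcome name, results at 3 and 9 months rest on one definition of dry and those at 6 and 12 months on another. A reader following continence over the year could then take a change of instrument for a change in the men.

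**Working it through.** The protocol gives no figure to reproduce. The check sets the outcome times against the instruments described for each time.

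| Months after randomisation | Subjective outcome (6.2) | Questionnaire with leakage items (5.1, Summary) | 3-day diary (5.2) | Other content listed (5.2, 6.5.1) |
|---|---|---|---|---|
| 3 | continence or improvement | no | yes | health care utilisation |
| 6 | continence or improvement | yes | yes | health care utilisation, SF-12, EQ-5D |
| 9 | continence or improvement | no | yes | health care utilisation |
| 12 | improvement (continence is the primary outcome) | yes | yes | health care utilisation, SF-12, EQ-5D |

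1. **Count.** Continence or improvement is promised at three times (3, 6 and 9 months), and two of them have no questionnaire. Including improvement at 12 months, it is two of four.

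2. **Does the protocol treat the diary as the subjective report?** Not in the text available. Section 6.2 labels diary episodes objective and lists them as a separate outcome. Section 6.5.5 ties subjective continence to the ICI questionnaire. The footnote to section 6.2 does use the change from wet to dry across the 3-monthly diaries, but for duration of incontinence, which is another outcome.

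3. **What can the diary give?** It records leakage episodes and quantity at 3, 6, 9 and 12 months, and a diary is also completed before randomisation (section 2.3). Wet/dry status over the diary days, and change from baseline, can therefore be derived at every time.

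4. **Would the two measures agree?** Not necessarily. Section 2.1 admits a man on any answer indicating loss of urine to either of two questions, so infrequent leakers are eligible. As an illustration only, assume that leaks follow a Poisson process. The probability of a dry 3-day diary is then exp(−3 × daily rate):
   - one leak a week: exp(−3 × 1/7) = exp(−0.429) = 0.65
   - two leaks a week: exp(−3 × 2/7) = exp(−0.857) = 0.42

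   Such a man could truthfully report leakage on a questionnaire and still return a dry diary. The protocol does not say how many men leak this rarely, so the effect on the overall proportion classed as dry cannot be calculated.

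**The case against.** The strongest reply is that the information is not lost. Men complete the diary themselves at 3 and 9 months, there is a baseline diary for comparison, and the footnote to section 6.2 already reads wet-to-dry change from the diaries. The same footnote plans to ask men which month they were last wet and for how long after the operation, which bears on their status at the intermediate times. This stands. A reader might infer that continence at 3 and 9 months cannot be obtained at all; the protocol does not support that. What is missing is a stated subjective item, not every source on continence.

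Second, the forms are in Appendix VI, which is not available here, and section 5.2 introduces its list in open terms. A short question in the 3- and 9-month mailing cannot be ruled out. This also stands, and it makes the finding conditional. If the item exists, one line in section 5.2 settles the matter.

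Third, the analysis plan could name the instrument for each time. That is true of naming it, but a plan cannot supply answers to a question that was never asked.

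Fourth, a reader might set the gap between diary and questionnaire against the 15-point difference the trial is designed to detect. That comparison is not supported. The 15 points are a difference between arms at 12 months. A change of instrument alters the level in both arms, and at any single time both arms are measured in the same way. The leak rates in the illustration are also assumed. Nor does the protocol promise one combined 3-6-9-12 month curve, so mixing the definitions is a risk to be closed off and not an error already made.

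**Conclusion.** The point holds in a limited form. The outcome list in section 6.2 and the collection schedule in sections 5.1, 5.2 and 6.5.1 do not match at 3 and 9 months. On the described content, those results can come only from the diary, which the protocol itself treats as a separate, objective measure. The conclusion assumes that the Appendix VI forms for those months carry no subjective continence or improvement item.

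The reach is two time points of one secondary outcome. The 12-month primary outcome, the sample size and the cost-effectiveness outcomes are untouched, as is the between-arm comparison at any single time. The point is still worth acting on: one of the two times is the reading nearest the end of therapy, the remedy is cheap, and an item not asked at the time cannot be recovered afterwards.

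**What to change.** First check the 3- and 9-month forms in Appendix VI. If they already carry a subjective continence item, say so in section 5.2. If they do not, reconcile sections 5.1, 5.2 and 6.2 in one of two ways:

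- **Add the items.** Put the two leakage questions already used for screening (how often, how much) into the 3- and 9-month mailings for men who have not yet passed those points. The cost is a slightly longer form. The protocol is at Version 6 of July 2007 and recruitment is well under way, so subjective data at 3 and 9 months would exist for later recruits only, and the report should say so.
- **Restrict the outcome.** Limit the subjective report to 6 and 12 months. This is a change of wording only, at the price of losing those two time points for this outcome.

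In either case, define diary-based continence (for example, no leakage recorded on the diary days) as a separate outcome at 3, 6, 9 and 12 months, name the instrument for each time point in section 6.2, and do not combine the two definitions in one time course.
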